### 1.3 Benefit/risk and ethical assessment

It is not expected that patients will derive any clinical benefit from treatment with AZD5069 over a period of one month. Potential risks have been identified through review of the clinical studies so far conducted, the GSAD (D3550C00001) and GMAD (D3550C00007) studies, as well as review of non-clinical animal studies with AZD5069 and of the literature and unpublished information relating to other CXCR2 antagonists. Risks to patients will be minimized by incorporating relevant exposure margins to animal toxicology findings and by regular monitoring.

The most relevant findings observed in the non-clinical studies with AZD5069 with potential relevance to humans were changes in the level of white blood cells. In the initial one-month dog study (20 mg/kg bd), dose-related increases were observed in white blood cells (mostly attributable to neutrophils) from Day 2. In addition, dose-related increases in globulin and C reactive protein (CRP) were noted in all dose groups with increases in CRP being generally highest on Day 2. The second one-month dog study was aimed to define a no observable adverse effect level (NOAEL) for changes in neutrophils and CRP and to understand the speed of onset and recovery from these changes. Increases in both parameters were observed from 24 hours after the first dose in all dogs dosed at 10 mg/kg bd and in individual animals dosed at 0.5 mg/kg bd. Following the cessation of dosing, both parameters returned to baseline levels during the recovery period. A dose level of 0.1 mg/kg bd was determined to be NOAEL for changes in neutrophils and CRP.

The major effect seen to date in the GSAD (D3550C00001) and GMAD (D3550C00007) studies has been a reduction in circulating neutrophils. This was dose-related in the GSAD and GMAD studies, with more subjects having reductions and for longer periods at higher doses. A reduction in neutrophils is an expected effect of a CXCR2 antagonist and was also seen with AZD8309 (see AZD8309 Investigator's Brochure (IB)) and with SCH527123 (Khalilieh et al 2007a), (Khalilieh et al 2007b), (Khalilieh et al 2007c). One subject, dosed with AZD5069 100 mg bd, was withdrawn from the GMAD (D3550C00007) study because of a reduction in circulating neutrophils below the specified limit of  $1.0 \times 10^9/L$  lasting for longer than 48 hours.

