### 3.2.4 Dose consideration and treatment duration

Two doses of AZD5069, 50 mg and 80 mg, bd, will be administered to COPD patients for 4 weeks.

These doses have been selected based upon established safety and tolerability in the GSAD and GMAD studies, and have been chosen to minimise the risk that patients will have drops in circulating neutrophils below  $1.0 \times 10^9/L$  for periods longer than 24 hours.

Following 100 mg bd dosing in the GMAD, 1 out of 6 healthy subjects had neutrophil counts which decreased below  $1.0 \times 10^9/L$ . Based on the PK/PD modelling done from the GSAD data, on 80 mg bd, 15% or less of the healthy subjects dosed would be expected to experience a neutrophil decrease below this limit that persists for more than 24 hours. Therefore this dose was chosen to be near the top of the dose response curve based on systemic neutrophil

decrease, where the large majority of COPD patients (whose neutrophil numbers will be elevated in comparison with healthy volunteers) would be expected to complete 1 month's dosing. 50 mg is a dose where no patients would be expected to withdraw due to decreases in neutrophils, according to the withdrawal criteria.

A treatment period of 4 weeks has been selected as this is considered sufficient to investigate safety and tolerability and will be supported with respect to toxicology.

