### **12.2.3 Safety and tolerability**

Safety data will be summarised based on the safety analysis set.

Continuous variables will be summarised using descriptive statistics (eg, n, mean, SD, min, median, max) by treatment group. Categorical variables will be summarised in frequency tables (frequency and proportion) by treatment group. Graphical presentations will be used as appropriate. Examples may include line graphs showing individual or mean development over time, shift plots showing baseline values on the horizontal axis and post-treatment values on the vertical axis.

Baseline will be the value measured and collected at Visit 2 prior to the first dose. If the measurement is missing, the latest pre-treatment measurement for each parameter will be

taken as baseline. For ECG parameters, vital signs and lung function tests, change from baseline at on- and post- treatment visits will be defined as: visit value-baseline value.

All adverse events will be collected for each patient from the time when informed consent is received until the follow-up visit (Visit 7). Adverse events will be considered as treatment emergent if they start or worsen on or after the first day of dosing, up to the post-study medical examination performed at Visit 7. AEs that occur before dosing will be reported separately. All AEs will be listed for each patient.

Adverse events will be summarised by PT (preferred term) and SOC (System organ class) using MedDRA vocabulary. Adverse events will also be summarised by causality and intensity, and causality and seriousness. Furthermore, listings of serious adverse events and adverse events that led to withdrawal will be made and the number of patients who had any adverse events, serious adverse events, adverse events that led to withdrawal, adverse events with severe intensity, other significant adverse events and deaths will be summarised.

ECG parameters will be summarised for the absolute values at each scheduled assessment, together with the corresponding changes from the baseline values. The QT correction factor will be based on the Fridericia's formula. Further categorical summaries of absolute QT and calculated QTcF values (>450 ms, >480 ms, >500 ms) and change from baseline values in QT and QTcF values (>30 ms, >60 ms) may also be produced.

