All laboratory data will be listed. Deviations from extended and standard reference ranges quoted in project reporting ranges, will be explicitly noted on these listings where applicable. For parameters where there are no extended or standard reference ranges the reference range from the local laboratory will be used. Numerical laboratory data will be summarised using standard summary statistics for each treatment group at each visit. The change from baseline value will be similarly summarised. Discrete laboratory data will be summarised showing the number of patients at each level of measurement at each visit by treatment group. Summaries of the number of patients falling outside the reference ranges at each time point will also be provided by treatment group. Separate listings of only those values falling outside these reference ranges will also be produced.

Neutrophil counts will be summarised for the absolute value at each scheduled assessment together with the corresponding changes from the baseline value and the % changes from the baseline value. In addition, the maximum change and maximum % change from the baseline value will be summarised together with the assessment time the maximum changed occurred.

The following plots (please also refer to Section 12.2.6) will also be provided:

- Plots of mean value at each dose level of AZD5069 and placebo against time, symbols indicating dose level - medians will be used instead of means if the data is not normally distributed

- Plots of absolute values vs time (one plot per treatment group per data type showing separate lines for each patient, with a reference line added at the upper reference limit)
- Plots of change from baseline value vs time (one plot per treatment group per data type showing separate lines for each patient)
- Plots of % change from baseline value vs time (one plot per treatment group per data type showing separate lines for each patient).

Additional plots may produced if appropriate.

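### Section 12.2.3 fixes an upper-limit reference line and an undirected maximum change for neutrophils, although the expected and dose-limiting effect is a fall

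*Protocol*

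**What the plan says.** Four statements in Protocol section 12.2.3 govern how neutrophils are displayed.

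- Individual absolute values are plotted against time, one plot per treatment group and data type, "with a reference line added at the upper reference limit". No lower line is mentioned.
- For neutrophils, "the maximum change and maximum % change from the baseline value will be summarised", together with the time at which it occurred. Neither a direction nor a time window is given.
- For laboratory data generally, "Summaries of the number of patients falling outside the reference ranges at each time point will also be provided by treatment group".
- A sign convention is given, but not for laboratory data: "For ECG parameters, vital signs and lung function tests, change from baseline at on- and post- treatment visits will be defined as: visit value-baseline value".

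Section 12.2.5 carries these methods over to circulating neutrophils as the pharmacodynamic variable.

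Other sections make clear which side matters. Section 1.3 states: "A reduction in neutrophils is an expected effect of a CXCR2 antagonist". Section 3.2.4 says the doses "have been chosen to minimise the risk that patients will have drops in circulating neutrophils below" 1.0 × 10⁹/L for longer than 24 hours. It adds that on 80 mg bd "15% or less of the healthy subjects dosed would be expected to experience a neutrophil decrease below this limit", persisting beyond 24 hours. Section 5.8 requires treatment to stop when a neutrophil count below 1.0 × 10⁹/L, or a leucocyte count below 2.0 × 10⁹/L, has not recovered on a repeat sample.

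**The concern.** The main expected safety signal is a low count. The one reference line fixed for the individual plots marks high counts, and the one extreme-value summary has no direction. A reader of the individual plots could not see who crossed the lower limit or 1.0 × 10⁹/L. A reader of the maximum-change table could not be sure of seeing the nadir.

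The study is meant to aid dose selection for later trials (sections 1.2 and 3.2.3), and the dose rationale predicts how often counts stay below 1.0 × 10⁹/L. Neither section 12.2.3 nor section 12.2.5 names that threshold. By contrast, section 12.2.3 lists optional cut-offs for QT and QTcF (450, 480 and 500 ms; changes of 30 and 60 ms), although section 1.1 rates the potential for QT prolongation as low.

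**Working it through.** **Inputs.** The display rules come from section 12.2.3, the expected direction from 1.3, the threshold and the 15% figure from 3.2.4, the stopping criterion from 5.8, the adverse event rules from 6.4.3, and about 20 patients per arm from the synopsis. The 15% comes from a PK/PD model whose parameters are not given, so it cannot be reproduced. Section 12.3 contains no sample size calculation to reproduce.

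**Step 1: what the maximum-change rule returns.** Let B be a patient's baseline, X(v) the count at visit v, and D(v) = X(v) − B.

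- Signed reading: max D(v). If every count is below baseline, this is the smallest fall. If any count is above baseline, it is a rise.
- Absolute reading: max |D(v)|. A rise, for example during an infection, that exceeds the fall replaces the nadir.
- Quantity needed: B − min X(v), taken over on-treatment visits.

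The % change, 100 × D(v)/B, has the same fault, because B is fixed within a patient and the visits rank in the same order. The missing window matters too. Leucocytes are measured at Visit 7, after treatment has ended. Section 1.1 gives a terminal half-life of about 11 hours and says the neutrophil effect follows plasma concentration. On the signed reading, a patient suppressed on treatment who recovers by Visit 7 has the maximum at Visit 7.

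**Step 2: how the threshold event reaches the output.**

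- Low count confirmed on repeat: treatment stops (5.8), a discontinuation adverse event is reported (6.4.3), and the patient enters the adverse event tables, the withdrawal listing and the count of patients with events leading to withdrawal (12.2.3). That count combines all causes.
- Low count that recovers on repeat: it need not become an adverse event (6.4.3), so as a threshold event it may appear only in a listing.
- Confirmatory repeat sample: it is unscheduled, while the neutrophil summaries cover scheduled assessments.

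**Step 3: what a direct count could show with n = 20 per arm.** Expected number = 20p; P(at least 1) = 1 − (1 − p)^20.

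| True rate p | Expected | P(at least 1) |
|---|---|---|
| 15% | 3.0 | 0.961 |
| 10% | 2.0 | 0.878 |
| 5% | 1.0 | 0.642 |

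At 15%, P(at least 2) = 0.824. Exact (Clopper-Pearson) 95% intervals: 0/20 gives 0 to 16.8% (upper limit 1 − 0.025^(1/20)); 1/20 gives 0.1 to 24.9%; 3/20 gives 3.2 to 37.9%. The 1 of 6 healthy subjects at 100 mg bd cited in section 3.2.4 (16.7%) has an interval of 0.4 to 64.1%.

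**Step 4: an out-of-range count without direction.** Assume a normal scale, a 95% reference range, and an arm 1 SD above mid-range that is shifted down by d SD. Then m = 1 − d, low = Φ(−1.96 − m) and high = 1 − Φ(1.96 − m). These shifts are assumptions, not protocol figures.

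| d | Low | High | Outside |
|---|---|---|---|
| 0 | 0.15% | 16.85% | 17.0% |
| 1 | 2.5% | 2.5% | 5.0% |
| 2 | 16.85% | 0.15% | 17.0% |
| 2.5 | 32.28% | 0.03% | 32.3% |

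If low and high were merged, a fall could lower the count, leave it unchanged or raise it. The equality at d = 2 is symmetric by construction. It shows only that a merged count cannot be read for direction.

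**The case against.** The strongest reply is that the fall would be visible anyway. Section 12.2.3 requires absolute, change and % change summaries at each scheduled assessment, with minimum and median among the example statistics. It also requires mean or median plots by dose and individual change and % change plots; all laboratory values are listed, and further plots are allowed. This stands, and it limits the point. A reader might infer that the planned displays would hide a neutrophil fall; the documents do not support that.

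Three other stronger readings also fail.

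- A reader might infer that the threshold event is never tabulated. Confirmed cases do reach the discontinuation counts and listing, and marked haematological abnormalities may be classed as other significant adverse events (11.1.1). Detailed tables are also commonly left to the SAP, which was not available here, so a missing table is not a fault in itself.
- A reader might infer that high and low values are pooled. The wording permits this but does not say it, and listings must flag each deviation.
- A reader might infer that the trial is too small because 0/20 does not exclude 15% at the two-sided 95% level. The trial tests no hypothesis and never set out to exclude that figure, which is a model prediction for healthy subjects. The one-sided 95% upper bound for 0/20, 1 − 0.05^(1/20) = 13.9%, lies below it.

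The plot list may be generic to all laboratory data, although it follows the neutrophil paragraph directly. An upper line has a purpose: sites are told of values above the upper limit (5.4.1), and neutrophils rose in dogs (1.3). That justifies keeping the upper line, not omitting a lower one. None of these replies repairs the maximum-change rule.

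**Conclusion.** The point holds as a moderate fault in text that the protocol itself fixes. The reference line is on the opposite side from the main expected safety signal. The maximum-change summary, on either reading and without a window, need not give the largest decrease. The event at 1.0 × 10⁹/L is visible only indirectly, and a low count that recovers may only be listed.

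No data are lost and no planned comparison is invalidated, so this is worth correcting but is not critical. The main gain is a readable count of the event behind the dose rationale: about 3 of 20 patients if the true rate at 80 mg bd were 15%. That number assumes 20 evaluable patients, that the healthy-subject ceiling carries over to COPD patients (section 3.2.4 expects their counts to be higher), and that confirmation on repeat stands in for persistence beyond 24 hours.

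**What to change.** Amend section 12.2.3 as follows, leaving the clinical stopping rule unchanged.

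1. On the individual absolute neutrophil plots, add reference lines at the lower limit of normal and at 1.0 × 10⁹/L alongside the upper limit.
2. Replace the maximum change and maximum % change with the on-treatment nadir and the maximum decrease from baseline (absolute and %), with the time of occurrence.
3. Report out-of-range counts separately for low and high values.
4. Tabulate by arm, descriptively and with exact 95% confidence intervals, the patients with any and with repeat-confirmed local-laboratory neutrophil counts below 1.0 × 10⁹/L and leucocyte counts below 2.0 × 10⁹/L, including unscheduled repeats.

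The cost is a wording change, two extra tables and changed plot lines. No new data or visits are needed.

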#### **12.2.4 Pharmacokinetics**

Listings and summary statistics for the derived parameters, along with figures will be provided as detailed in the PK/PD analysis plan.

#### **12.2.5 Pharmacodynamics**

Circulating neutrophils will be summarised using the methods described in Section 12.2.3 and will be based on the safety analysis set. In the unlikely event that the safety analysis set and the PD analysis set are very different, summaries may also be produced based on the PD analysis set. This will be determined at blind review.

#### **12.2.6 Pharmacokinetics/Pharmacodynamics**

Graphical representation of the data will be detailed in the PK/PD analysis plan.

### **12.3 Determination of sample size**

Formal sample size calculations have not been performed for this study, since no formal statistical hypothesis testing will be performed. A sample size of 60 is considered adequate to investigate short term safety and tolerability in this patient population.

### **12.4 Data monitoring committee (Not applicable)**

Not applicable.

#### 13.2 Overdose

For the purpose of this study an overdose is defined as any dose of investigational product above that which is mandated within the protocol. There is no experience of overdose and no antidote to AZD5069. In cases of known or suspected overdose, symptomatic treatment and monitoring of vital functions should be performed according to routine clinical practice.

- An overdose with associated AEs is recorded as the AE diagnosis/symptoms on the relevant AE modules in the eCRF and on the overdose eCRF module. If the AE meets the criteria for an SAE, it should also be recorded on the SAE module.
- An overdose without associated symptoms is only reported on the overdose eCRF module.

If an overdose on an AstraZeneca study drug occurs in the course of the study, then investigators or other site personnel inform appropriate AstraZeneca representatives **within one day**, ie, immediately but no later than **the end of the next business day** of when he or she becomes aware of it.

The designated AstraZeneca representative works with the investigator to ensure that all relevant information is provided to the AstraZeneca Patient Safety data entry site.

For overdoses associated with SAE, standard reporting timelines apply, see Section 6.4.4. For other overdoses, reporting should be done within 30 days.

### 13.3 Pregnancy

All outcomes of pregnancy should be reported to AstraZeneca.

#### 13.3.1 Maternal exposure

Women of childbearing potential are not allowed to be included in this study (refer to Section 4.1). Should a pregnancy still occur, the investigational product should be discontinued immediately, the patient withdrawn from the study and the pregnancy reported to AstraZeneca.

Pregnancy itself is not regarded as an adverse event unless there is a suspicion that the investigational product under study may have interfered with the effectiveness of a contraceptive medication. Congenital abnormalities/birth defects and spontaneous miscarriages should be reported and handled as SAEs. Elective abortions without complications should not be handled as AEs. All initial reports and outcomes of pregnancies (spontaneous miscarriage, elective termination, ectopic pregnancy, normal birth or congenital abnormality) should be followed up and documented even if the patient was discontinued from the study.

If any pregnancy occurs in the course of the study, then investigators or other site personnel inform appropriate AstraZeneca representatives **within one day** ie, immediately but no later than the **end of the next business day** of when he or she becomes aware of it.

The designated AstraZeneca representative works with the investigator to ensure that all relevant information is provided to the AstraZeneca Patient Safety data entry site within 1 day for fatal and life threatening events or 5 days for all other SAEs, see Section 6.4.4, and within 30 days for all other pregnancies.

The same timelines apply when outcome information is available.

The pregnancy module in the eCRF is used to report the pregnancy together with a pregnancy fax report page which is sent to Patient Safety when a pregnancy is identified. The Pregnancy Outcome Report is used to report the outcome of the pregnancy. These reports should be sent through to the Data Entry Site within 30 calendar days of the Investigator becoming aware.

#### 13.3.2 Paternal exposure

Male patients must refrain from fathering a child during the study and 3 months following the last dose (refer to Section 5.1).

Pregnancy of a patient's partner is not considered to be an adverse event. However, the outcome of any pregnancy occurring from the date of the first dose until 3 months after the last dose must be reported to AstraZeneca **within 5 days** and documented as specified in Section 13.3.1.

## **FURTHER GUIDANCE ON THE DEFINITION OF A SERIOUS ADVERSE EVENT (SAE)**

### **Life threatening**

‘Life-threatening’ means that the subject was at immediate risk of death from the AE as it occurred or it is suspected that use or continued use of the product would result in the subject’s death. ‘Life-threatening’ does not mean that had an AE occurred in a more severe form it might have caused death (eg, hepatitis that resolved without hepatic failure).

### **Hospitalisation**

Outpatient treatment in an emergency room is not in itself a serious AE, although the reasons for it may be (eg, bronchospasm, laryngeal oedema). Hospital admissions and/or surgical operations planned before or during a study are not considered AEs if the illness or disease existed before the subject was enrolled in the study, provided that it did not deteriorate in an unexpected way during the study.

### **Important medical event or medical intervention**

Medical and scientific judgement should be exercised in deciding whether a case is serious in situations where important medical events may not be immediately life threatening or result in death, hospitalisation, disability or incapacity but may jeopardize the subject or may require medical intervention to prevent one or more outcomes listed in the definition of serious. These should usually be considered as serious.

Simply stopping the suspect drug does not mean that it is an important medical event; medical judgement must be used.

Examples of such events are:

- Angioedema not severe enough to require intubation but requiring iv hydrocortisone treatment
- Hepatotoxicity caused by paracetamol (acetaminophen) overdose requiring treatment with N-acetylcysteine
- Intensive treatment in an emergency room or at home for allergic bronchospasm
- Blood dyscrasias (eg, neutropenia or anaemia requiring blood transfusion, etc) or convulsions that do not result in hospitalisation
- Development of drug dependency or drug abuse.

